## **9.2 Safety Scales**

### **9.2.1 Abnormal Involuntary Movement Scale (AIMS)**

The AIMS is a clinician-rated assessment of abnormal movements consisting of unobtrusive observation of the subject at rest (with shoes removed) and several questions or instructions directed toward the subject. Using a severity scale ranging from 0 (none) to 4 (severe), clinicians rate dyskinesia in several body regions, including the facial area, extremities, and trunk.

### **9.2.2 Barnes Akathisia Rating Scale (BAS)**

The BAS is a rating scale geared toward assessment of neuroleptic-induced akathisia, though it can be used to measure akathisia associated with other drugs as well. [30, 31]. The BAS will be administered by a qualified rater at the site.

### **9.2.3 Simpson-Angus Scale (SAS)**

The SAS is a clinician-rated assessment of neuroleptic-induced Parkinsonism consisting of 10 items. Items are anchor-based, rated on a 5-point scale and address rigidity, gait (bradykinesia), tremor, glabellar tap, and salivation [32]. The SAS will be administered by a qualified rater at the site.

### **9.2.4 Columbia Suicide Severity Rating Scale**

The C-SSRS was developed by a team of researchers at Columbia University to address the need for standardized classification of suicide reports to assess suicide risk. This scale consists of a baseline evaluation that assesses the lifetime experience of the subject with suicide events and suicidal ideation and a post-baseline evaluation that focuses on suicidality since the last study visit. A baseline C-SSRS will be completed at the screening visit. The C-SSRS Since Last Visit form will be completed at all subsequent visits.

## **10.0 REMOVAL OF SUBJECTS FROM STUDY**

Individuals can be taken off the study treatment and/or study at any time at their own request, or they may be withdrawn at the discretion of the investigator for safety, behavioral or administrative reasons. The reason(s) for discontinuation will be documented and may include:

- Individual voluntarily withdraws from treatment (follow-up permitted);
- Individual withdraws consent (termination of treatment and follow-up);
- Individual is unable to comply with protocol requirements;
- Individual experiences toxicity that makes continuation in the protocol unsafe;
- Physician judges continuation on the study would not be in the patient's best interest;
- Individual becomes pregnant (pregnancy to be reported along same timelines as a serious adverse event).

## **11.0 ADVERSE EVENTS**

During the first week, common side effects are a slight drowsiness and a feeling of increased blood flow in the head. As with any mineral product, people with kidney deficiency should not take this product. Some individuals have reported dizziness or slight headaches when first taking MMFS-202-302.

### **11.1 Contraindications:**

None

### **11.2 Special Warnings and Precautions for Use**

None

### **11.3 Interaction with other medications**

None.

### **11.4 Adverse Event Monitoring**

Adverse event data collection and reporting, which are required as part of every clinical trial, are done to ensure the safety of subjects enrolled in the studies as well as those who will enroll in future studies using similar agents. Adverse events are reported in a routine manner at scheduled times during a trial. Additionally, certain adverse events must be reported in an expedited manner to allow for optimal monitoring of patient safety and care.

All individuals experiencing an adverse event, regardless of its relationship to study drug/device, will be monitored until:

- the adverse event resolves or the symptoms or signs that constitute the adverse event return to baseline;
- any abnormal laboratory values have returned to baseline;
- there is a satisfactory explanation other than the study drug for the changes observed; or
- death.

### **11.5 Definitions**

#### **11.5.1 Definition of Adverse Event**

An adverse event (AE) is any untoward medical occurrence in a patient receiving study treatment and which does not necessarily have a causal relationship with this treatment. An AE can therefore be any unfavorable and unintended sign (including an abnormal laboratory finding), symptom, or disease temporally associated with the use of an experimental intervention, whether or not related to the intervention.

#### **11.5.2 Severity of Adverse Events**

The severity of an AE is graded as follows:

Mild (grade 1): the event causes discomfort without disruption of normal daily activities.

Moderate (grade 2): the event causes discomfort that affects normal daily activities.

Severe (grade 3): the event makes the patient unable to perform normal daily activities or significantly affects his/her clinical status.

Life-threatening (grade 4): the patient was at risk of death at the time of the event.

Fatal (grade 5): the event caused death.

#### **11.5.3 Serious Adverse Events**

A “serious” adverse event is defined in regulatory terminology as any untoward medical occurrence that:

- Results in death.
  - If death results from (progression of) the disease, the disease should be reported as event (SAE) itself.
- Is life-threatening.
  - (the patient was at risk of death at the time of the event; it does not refer to an event that hypothetically might have caused death if it were more severe).
- Requires in-patient hospitalization or prolongation of existing hospitalization for  $\geq 24$  hours judged to be caused by study medication or procedures.
- Results in persistent or significant disability or incapacity.
- Is a congenital anomaly/birth defect
- Is an important medical event

Any event that does not meet the above criteria, but that in the judgment of the investigator jeopardizes the patient, may be considered for reporting as a serious adverse event. The event may require medical or surgical intervention to prevent one of the outcomes listed in the

definition of "Serious Adverse Event."

For example: allergic bronchospasm requiring intensive treatment in an emergency room or at home; convulsions that may not result in hospitalization; development of drug abuse or drug dependency.

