## 11.6 Steps to Determine If an Adverse Event Requires Expedited Reporting

Step 1: Identify the type of adverse event

Step 2: Grade the adverse event

Step 3: Determine whether the adverse event is related to the protocol therapy

Attribution categories are as follows:

- Definite – The AE is *clearly related* to the study treatment.
- Probable – The AE is *likely related* to the study treatment.
- Possible – The AE *may be related* to the study treatment.
- Unrelated – The AE is *clearly NOT related* to the study treatment.

Note: This includes all events that occur within 30 days of the last dose of protocol treatment. Any event that occurs more than 30 days after the last dose of treatment and is attributed (possibly, probably, or definitely) to the agent(s) must also be reported accordingly.

Step 4: Determine the prior experience of the adverse event.

Expected events are those that have been previously identified as resulting from administration of the agent. An adverse event is considered unexpected, for expedited reporting purposes only, when either the type of event or the severity of the event is not listed in:

- the current known adverse events listed in the Agent Information Section of this protocol;
- the GRAS dossier for the supplement;

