## 11.7 Reporting Requirements for Adverse Events

Expedited

- The Principal Investigator must be notified within 24 hours of learning of any serious adverse events, regardless of attribution, occurring during the study or within 30 days of the last administration of the study drug.
- The investigator will inform the sponsor within 24 hours of notification of any serious adverse event by phone or fax, with follow-up with a written narrative of the event within 48 hours.
- The Northwestern University Institutional Review Board must be notified within 10 business days of "any unanticipated problems involving risk to subjects or others"

The following events meet the definition of UPR:

1. Any serious event (injuries, side effects, deaths or other problems), which in the opinion of the Principal Investigator was unanticipated, involved risk to subjects or others, and was possibly related to the research procedures.
2. Any serious accidental or unintentional change to the IRB-approved protocol that alters the level of risk.
3. Any deviation from the protocol taken without prior IRB review to eliminate apparent immediate hazard to a research subject.
4. Any new information (e.g., publication, safety monitoring report, updated sponsor safety report), interim result or other finding that indicates an unexpected change to the risk/benefit ratio for the research.
5. Any breach in confidentiality that may involve risk to the subject or others.
6. Any complaint of a subject that indicates an unanticipated risk or that cannot be resolved by the Principal Investigator.

- The FDA will be notified within 7 business days of any unexpected fatal or life-threatening adverse event with possible relationship to study drug, and 15 business days of any event that is considered: 1) serious, 2) unexpected, and 3) at least possibly related to study participation.

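### Section 11.5.3 makes hospitalization alone depend on causality, so an unrelated admission may not require prompt notice to the PI and sponsor

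*Combined protocol and SAP*

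**What the plan says.** Section 11.5.3 defines seriousness by six bullets: death, threat to life, hospitalization, disability, congenital anomaly, and a last one worded "Is an important medical event". The hospitalization bullet names a new in-patient stay or the prolongation of an existing one, sets a threshold of 24 hours, and ends "hours judged to be caused by study medication or procedures". A paragraph after the list adds that an event outside these criteria which "in the judgment of the investigator jeopardizes the patient, may be considered for reporting as a serious adverse event".

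The neighbouring sections treat causality separately:

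- Section 11.5.1 defines an adverse event as something that "does not necessarily have a causal relationship with this treatment".
- Section 11.6 gives relatedness its own place: "Step 3: Determine whether the adverse event is related to the protocol therapy".
- Section 11.7 requires the PI to be told within 24 hours of any SAE, "regardless of attribution, occurring during the study or within 30 days of the last administration of the study drug". The sponsor must be told within 24 hours of notification of an SAE, with a written narrative within 48 hours.
- Section 9.1.11 ties immediate sponsor notification to whether the event meets the SAE criteria.
- Routine Reporting, under section 11.7, sends all other adverse events to an annual report.

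**The concern.** Seriousness describes the outcome of an event, and relatedness is a separate judgment about its cause. The protocol keeps the two apart for five of its six criteria and merges them for hospitalization. The PI notice in section 11.7 applies whatever the attribution, but only to events that are already SAEs. A causality condition inside the definition acts before that rule can.

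What is at stake is how quickly someone outside the study team hears of an admission. Under section 13.0, safety is monitored by the PI with oversight by co-investigator clinicians, so the sponsor notice is a main outside check on single events. In this population an admission for psychiatric worsening could readily be put down to the illness. An initial judgment that an admission is unrelated would then also decide whether the sponsor is told promptly.

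**Working it through.** There is no figure in the plan to reproduce. The check is a count and a trace through the sections.

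**1. Count the criteria in section 11.5.3.**

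| Criterion | Causality condition |
|---|---|
| Death | No |
| Life-threatening | No |
| Hospitalization, new or prolonged | Yes |
| Disability or incapacity | No |
| Congenital anomaly | No |
| Important medical event | No |

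Total 6; with a condition 1; without 6 − 1 = 5.

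**2. Set out the two readings.** The hospitalization bullet has 2 parts, new admission and prolongation.

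- *Broad reading:* the closing phrase governs the whole bullet, so it reaches 2 of 2 parts.
- *Narrow reading:* the phrase attaches only to prolongation, which it directly follows, so it reaches 1 of 2 parts. Every new admission is then an SAE, and only an unrelated prolongation drops out.

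**3. Trace one event on the broad reading.** Take an admission rated Unrelated, which is 1 of the 4 attribution categories in section 11.6, and suppose it meets none of the other five criteria.

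- Section 11.5.3: the causality condition fails, so the bullet is not met. The paragraph after the list is permissive, so the event becomes an SAE only if the investigator chooses.
- Section 11.7, PI notice: it applies to SAEs, so it is not mandatory.
- Section 11.7, sponsor notice: also tied to SAE status, so neither the 24-hour notice nor its 48-hour narrative is mandatory. Section 9.1.11 gives the same result.
- Routine Reporting: the event goes to the annual report.

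The loss is one PI notice and one sponsor stream, the stream being the initial notice and its narrative.

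**4. List what does not change.**

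- Recording: section 9.1.11 records adverse events during participation whatever their suspected cause.
- Follow-up: section 11.4 requires monitoring of anyone with an adverse event, related or not.
- Analysis: the comparison of adverse events between arms in section 3.0 still includes the event.
- FDA notices and item 1 of the IRB list in section 11.7: both already require at least possible relatedness, so an unrelated event triggers neither in any case.

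**The case against.** The strongest reply is that the narrow reading is grammatically sound and leaves little to correct. That stands as a limit on the size of the point. It does not remove it, because the bullet does not say which reading is meant and the classification of a new unrelated admission depends on it.

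A second reply is that other routes catch the event. An assessor may call it an important medical event, a criterion with no causality condition, or use the paragraph after the list. Both are possible, so the accurate statement is that the notices are not required, not that they will never be sent. Neither route makes a notice mandatory for every unrelated admission.

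A third reply is that attribution already governs parts of expedited reporting: it is a step in section 11.6, it is a condition of the FDA notice and of IRB item 1, and it appears in Routine Reporting. This is correct, so the clause is not out of keeping with all of section 11. The note in section 11.6 says "This includes all events that occur within 30 days of the last dose of protocol treatment" and then adds "Any event that occurs more than 30 days after the last dose of treatment and is attributed" to the agent, which suggests that attribution is meant to filter only later events. What the opening word of that note refers to is unclear, so it carries little weight. The firm comparison is with the PI notice in section 11.7, which expressly sets attribution aside.

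The PI notice is also largely nominal as a loss, since section 9.1.11 already has the PI or a designee assess every adverse event. Planned exposure is modest as well: 60 patients × 9 weeks = 540 person-weeks, about 10 person-years.

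**Conclusion.** The point holds as a drafting fault that should be corrected. One of six seriousness criteria carries a causality condition. On the broad reading this makes the PI notice and the sponsor notice with its narrative non-mandatory for some unrelated admissions. The main loss is prompt sponsor notice.

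That outcome needs four things together: the broad reading, a rating of Unrelated, no other criterion met, and the discretionary paragraph not used. On the narrow reading the gap is small, but two assessors could still classify the same event differently. The documents give no hospitalization rate, so the number of affected events cannot be estimated.

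Three stronger readings are tempting and are not supported:

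- *Sections 11.5.3 and 11.7 contradict each other.* They can be applied in sequence, definition first and notice second. The clause narrows what the PI notice covers without conflicting with it.
- *Admissions would be lost from the safety comparison.* During participation they are recorded and compared as adverse events. Nothing is claimed about the record after participation ends.
- *Admissions rated Possible would also lose their serious label, and with it FDA reporting.* The protocol does not say which attribution categories satisfy the hospitalization clause, so the point is confined to Unrelated.

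**What to change.** In the hospitalization bullet of section 11.5.3, delete the causality condition, that is, everything after the first word of "hours judged to be caused by study medication or procedures". Leave relatedness to Step 3 of section 11.6. If planned or social admissions are not meant to count as serious, exclude them by name in section 11.5.3 and not through a judgment about cause.

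This is a one-line protocol amendment. The cost is some additional SAE reports, number unknown. Without a named exclusion these could include planned or social stays of 24 hours or more. The planned adverse event analysis does not change.

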## 11.6 Steps to Determine If an Adverse Event Requires Expedited Reporting

Step 1: Identify the type of adverse event

Step 2: Grade the adverse event

Step 3: Determine whether the adverse event is related to the protocol therapy

Attribution categories are as follows:

- Definite – The AE is *clearly related* to the study treatment.
- Probable – The AE is *likely related* to the study treatment.
- Possible – The AE *may be related* to the study treatment.
- Unrelated – The AE is *clearly NOT related* to the study treatment.

Note: This includes all events that occur within 30 days of the last dose of protocol treatment. Any event that occurs more than 30 days after the last dose of treatment and is attributed (possibly, probably, or definitely) to the agent(s) must also be reported accordingly.

Step 4: Determine the prior experience of the adverse event.

Expected events are those that have been previously identified as resulting from administration of the agent. An adverse event is considered unexpected, for expedited reporting purposes only, when either the type of event or the severity of the event is not listed in:

- the current known adverse events listed in the Agent Information Section of this protocol;
- the GRAS dossier for the supplement;

## 11.7 Reporting Requirements for Adverse Events

Expedited

- The Principal Investigator must be notified within 24 hours of learning of any serious adverse events, regardless of attribution, occurring during the study or within 30 days of the last administration of the study drug.
- The investigator will inform the sponsor within 24 hours of notification of any serious adverse event by phone or fax, with follow-up with a written narrative of the event within 48 hours.
- The Northwestern University Institutional Review Board must be notified within 10 business days of "any unanticipated problems involving risk to subjects or others"

The following events meet the definition of UPR:

1. Any serious event (injuries, side effects, deaths or other problems), which in the opinion of the Principal Investigator was unanticipated, involved risk to subjects or others, and was possibly related to the research procedures.
2. Any serious accidental or unintentional change to the IRB-approved protocol that alters the level of risk.
3. Any deviation from the protocol taken without prior IRB review to eliminate apparent immediate hazard to a research subject.
4. Any new information (e.g., publication, safety monitoring report, updated sponsor safety report), interim result or other finding that indicates an unexpected change to the risk/benefit ratio for the research.
5. Any breach in confidentiality that may involve risk to the subject or others.
6. Any complaint of a subject that indicates an unanticipated risk or that cannot be resolved by the Principal Investigator.

- The FDA will be notified within 7 business days of any unexpected fatal or life-threatening adverse event with possible relationship to study drug, and 15 business days of any event that is considered: 1) serious, 2) unexpected, and 3) at least possibly related to study participation.

### Routine Reporting

- All other adverse events- such as those that are expected, or are unlikely or definitely not related to the study participation- are to be reported annually as part of regular data submission.

### 11.8 Unblinding Procedures

The blind should not be broken unless subject has completed all study procedures and the data has been locked. Emergency unblinding is expected to be infrequent.

Emergency unblinding should occur only if the principal investigator (or other treating physician) considers breaking the blind medically relevant. All subjects who have the blind broken will be discontinued from the study. Documentation of the reasons for unblinding, including date and time will be recorded in the source documents and the electronic case report form (eCRF).

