### **9.1.11 Adverse Event (AE) Monitoring**

The PI or a designee (eg, a licensed, qualified medical practitioner such as a physician's assistant or a nurse practitioner) listed on the site delegation of authority log must assess the severity and relationship to study medication(s) of all AEs. All observed or volunteered AEs regardless of treatment group or suspected causal relationship to the investigational product(s) will be recorded on the AE page(s) of the eCRF.

For all AEs, the investigator must pursue and obtain information adequate both to determine the outcome of the AE and to assess whether it meets the criteria for classification as an SAE requiring immediate notification to the Sponsor or its designated representative.

For all AEs, sufficient information should be obtained by the investigator to determine the causality of the AE. The investigator is required to assess causality and indicate that assessment on the eCRF. For AEs with a causal relationship to the investigational product, follow-up by the investigator is required until the event or its sequelae resolve or stabilize at a level acceptable to the investigator.

Adverse events (serious and non-serious) should be recorded on the CRF from the date the informed consent form (ICF) was signed until the end of their participation in the study, ie, the subject has discontinued or completed the study.

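### Section 11.8 ends study participation, not only treatment, for every unblinded patient, so Week 9 efficacy and safety measurements are lost and case report form recording of new adverse events stops early

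*Combined protocol and SAP*

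**What the plan says.** Section 11.8 restricts the trigger and sets the consequence. On the trigger: "Emergency unblinding should occur only if the principal investigator (or other treating physician) considers breaking the blind medically relevant". On frequency: "Emergency unblinding is expected to be infrequent". On the consequence: "All subjects who have the blind broken will be discontinued from the study". It also requires the reasons, date and time of unblinding to be documented in the source documents and the eCRF. It says nothing about later visits.

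Section 10.0 treats leaving treatment and leaving the study as different things. One listed reason is "Individual voluntarily withdraws from treatment (follow-up permitted"; withdrawal of consent, listed separately, ends both treatment and follow-up.

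On adverse events, three periods appear:
- Section 9.1.11 has events recorded on the CRF from consent "until the end of their participation in the study, ie, the subject has discontinued or completed the study". For events causally related to the product, the same section says that "follow-up by the investigator is required until the event or its sequelae resolve or stabilize at a level acceptable to the investigator".
- Section 11.4 says: "All individuals experiencing an adverse event, regardless of its relationship to study drug/device, will be monitored until" one of its listed end points is reached (resolution or return to baseline, laboratory values back to baseline, another satisfactory explanation, or death).
- Sections 11.6 and 11.7 cover events and serious events up to 30 days after the last dose, and later ones under 11.6 if attributed to the agent.

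Section 9.1.2 places the MCCB at baseline and end of study only, and Section 9.1.6 does the same for the CGI. The Schedule of Assessments in Appendix 1 gives ECG, safety laboratory tests and blood magnesium one post-dose time point, the final visit.

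**The concern.** The blind is broken after randomisation and for a medical reason, so the missing data that follow are not a chance loss. If such reasons arose more often on one arm, the loss would fall more on that arm. The documents give no information on whether they would.

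Most of the affected measurements have no second chance. The primary endpoint, the secondary endpoint (CGI-C), the ECG, the safety laboratory tests and magnesium are each measured after dosing only at the final visit. No early-termination version of any of them is stated. An unblinded patient still belongs to the safety population in Section 3.0, which needs only one exposure and a later contact with staff, but would contribute no scheduled post-dose ECG, laboratory or magnesium result to the between-arm comparison. Sections 13.0 and 14.11 name hypermagnesemia, with cardiac arrhythmias among its symptoms, as a rare but serious risk, so these are the measurements one would want.

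The length of CRF adverse-event recording is a related matter. It ends at discontinuation, while other sections follow or report events for longer.

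**Working it through.** **Reading the sections together**

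1. Section 11.8 says *study*. Section 10.0 shows that the protocol distinguishes study from treatment, so the text of 11.8 cannot be assumed to mean treatment only.
2. Discontinuation from the study before Week 9 means no final visit. Section 9.1.8 asks for an attempt at a final physical examination after discontinuation for any reason, but mentions no MCCB, CGI, ECG or laboratory test.
3. Under Section 8.1 the patient has not completed all visits and leaves the per-protocol set, which is analysed first. In the intent-to-treat analysis with LOCF, the only earlier MCCB is baseline, so the change is scored as zero.
4. An event that prompts unblinding starts before discontinuation, so it falls inside the CRF window of 9.1.11, and the same section requires its outcome to be pursued. What falls outside the window is a new event that starts after discontinuation. Sections 11.6 and 11.7 still expect such events to be assessed or notified for 30 days after the last dose.

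**The plan's own figures**

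Inputs from Section 8.1: difference 5 points, SD of change 6.5 in each arm, two-sided alpha 0.05, power 80%, 30 recruited per arm, attrition up to 20% (30 × 0.8 = 24 left).

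A two-sample t-test on change, with standardised difference 5/6.5 = 0.769, needs 27.5 per arm, so 28. Power is 83.4% at 30 per arm and 74.2% at 24. This reproduces the stated 28 per arm and 74-83%.

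**Size of the loss under LOCF (illustration)**

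The documents give no unblinding rate. Assume that k of 30 MMFS patients and no placebo patients are unblinded before Week 9. With p = k/30:

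- expected difference d = 5(1 − p)
- MMFS variance of change = (1 − p) × 6.5² + p(1 − p) × 5²
- pooled SD = √[(6.5² + MMFS variance)/2]
- power from the t-test at d/pooled SD, 30 per arm

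For k = 1: p = 0.0333, d = 4.83, MMFS variance = 40.84 + 0.81 = 41.65, pooled SD = √[(42.25 + 41.65)/2] = 6.48, standardised difference = 0.746.

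| k | d | MMFS SD | Power, LOCF | Power if excluded |
|---|---|---|---|---|
| 0 | 5.00 | 6.50 | 83.4% | 83.4% |
| 1 | 4.83 | 6.45 | 81.1% | 82.7% |
| 2 | 4.67 | 6.40 | 78.7% | 82.0% |
| 3 | 4.50 | 6.35 | 76.1% | 81.3% |

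The last column drops the k patients and assumes that their exclusion is unrelated to outcome. Each patient is 1/30 = 3.3% of an arm.

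**The case against.** A reader might infer that Section 11.8 contradicts Section 11.4 outright, so that a site cannot obey both. The documents do not support this. Section 11.8 says nothing about ending adverse-event monitoring, and 11.4 makes no exception for discontinued patients. A site can discontinue a patient and go on monitoring the event. The mismatch comes from the CRF window in 9.1.11, and it applies to anyone who completes or discontinues; unblinding is one route into it.

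A reader might also infer that safety follow-up is lost, or that the course of the prompting event disappears from the CRF. That too goes beyond the text, given the duty to pursue outcomes in 9.1.11, the 30-day notification in 11.7 and the attempted final examination in 9.1.8.

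A third tempting inference is that the rule removes the patients with the worst tolerability. The stated trigger is medical relevance, with no severity threshold, so this is conjecture.

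Two further objections have force. First, the lead analysis is per-protocol and requires all visits and 80-120% compliance. A retained patient who had stopped the tablets early would generally still be excluded, so the efficacy gain is confined mainly to the LOCF analysis. Second, ending participation at unblinding keeps unblinded ratings of CGI-C, PANSS and BNSS out of the data, and the principal investigator may be the one who breaks the blind. This is a real cost of retaining patients. It bears much less on ECG, laboratory and magnesium values.

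What remains is that 11.8 discards final-visit data that the protocol already schedules, and that the end of CRF recording does not match the other sections.

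**Conclusion.** The point holds in a limited form. Section 11.8 removes unblinded patients from the study, whereas Section 10.0 allows treatment withdrawal with follow-up. As written, this costs the Week 9 MCCB and CGI-C and the only scheduled post-dose ECG, safety laboratory and magnesium results. Through 9.1.11 it also ends CRF recording of new adverse events earlier than 11.4, 11.6 and 11.7 imply.

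The efficacy effect is small. Under the one-arm assumption above, each of the first three unblinded MMFS patients takes about 0.17 points off the expected LOCF difference and between 2 and 3 percentage points off power. The safety effect concerns few patients, but for each of them every scheduled post-dose ECG, laboratory and magnesium value is missing. No figure in the plan is shown to be wrong.

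The conclusion assumes that *discontinued from the study* means what it says and that no early-termination assessments are specified elsewhere. If the intended meaning is treatment only, the wording still needs correcting.

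**What to change.** Reconcile Sections 9.1.11, 10.0, 11.4, 11.6, 11.7 and 11.8 so that breaking the blind does not by itself end data collection:

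- State in 11.8 whether *discontinued* refers to treatment or to the study, and provide that patients who still consent keep the already scheduled assessments, including Week 9.
- Align the end of CRF adverse-event recording in 9.1.11 with the follow-up in 11.4 and the 30-day periods in 11.6 and 11.7, for all patients.
- Flag unblinded patients in the data set and plan a sensitivity analysis of the intent-to-treat results with and without their post-unblinding ratings.
- Keep raters unaware of the assignment where possible, and record when this was not possible.

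Whether study treatment continues after unblinding is for the sponsor and investigator to decide.

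The cost is a wording amendment, with no new visits or procedures. The downside is a few ratings made after the patient or the investigator knows the arm. The flag and the sensitivity analysis make these visible but do not remove the possible bias.
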